### 7.2.2 Secondary Endpoints

- Describe anti-tumor responses to CART-19 cell infusions.
  - i. For subjects with active disease, typical response criteria for partial response (PR) or complete response (CR) will be determined. Response determination will be only “descriptive” given the small number of subjects to be treated.
  - ii. For subjects treated with MRD (identified by PCR analysis of blood or marrow), determine elimination of MRD scored as yes/no.
  - iii. For subjects treated in remission, describe progression-free survival (PFS).
- Describe overall survival and cause of death
- Rates of grade 2, 3 and 4 GVHD
- For patients with banked or accessible tumor cells (such as patients with active CLL, ALL, etc) determine if *in vitro* cell killing assays of CART-19 cells against patient tumor correlates with clinical response.
- Determine if host immunity develops against the murine anti-CD19, and assess correlation with loss of detectable CART-19 (loss of engraftment).
- For patients with stored or accessible tumor cells, evaluate the post infusion tumor response in comparison to baseline responses prior to cytoreductive chemotherapy (week -4), to evaluate the effect on general anti-tumor immunity.
- In subjects infused with mixtures of CART-19 TCR $\zeta$  and TCR $\zeta$ :4-1BB cells, RT-PCR analysis of whole blood will be used to detect and quantify relative survival of CART-19 TCR $\zeta$  and TCR $\zeta$ :4-1BB cells over time.
- Determine the relative subsets of CART-19 T cells (Tcm, Tem, and Treg)

### 7.2.3 Exploratory Endpoints

- Describe the correlation of test expansion results with manufacturing feasibility and clinical outcome.

### 7.3 Sample Size

This is a 86 patient phase I/IIa study with an anticipated dropout rate of 20%. If this exploratory study suggests that one vector persists and engrafts better than the other vector, then a larger follow-on trial will be designed that has the statistical power to assess the potential efficacy of that vector.

CONFIDENTIAL

#### 7.4 Safety

This trial will infuse up to 72 patients. This may require enrollment of more subjects because of the dropout rate. In order to assess the confidence with which we can obtain an initial estimate on the toxicity rate in each cohort, the table below presents the exact 95% confidence intervals for the toxicity rate based on the first 7 or 10 subjects

n=7 Evaluable Subjects		n=10 Evaluable Subjects	
Observed Toxicity Rate	95% Exact Confidence Interval	Observed Toxicity Rate	95% Exact Confidence Interval
0% (0/7)	(0%, 41%)	0% (0/10)	(0%, 31%)
14% (1/7)	(0%, 58%)	10% (1/10)	(0%, 45%)
29% (2/7)	(4%, 71%)	20% (2/10)	(3%, 56%)
43% (3/7)	(10%, 82%)	30% (3/10)	(7%, 65%)

With 10 subjects and a true underlying toxicity rate of 20%, the probability of failing to observe an adverse event is 11%. The probability decreases to 3% if the true toxicity rate is 30%. Taking into account potential drop out due to disease progression either prior to infusion or before the planned response assessment is possible, with seven subjects the probability of failing to observe an adverse event is 21%, if the true toxicity rate is 20% and decreases to 8% if the true toxicity rate is 30%.

#### 7.5 Efficacy

Anti-tumor activity will be assessed as a secondary trial endpoint. Anti-tumor efficacy of CART-19 cells will be determined in a follow-on study.

Another exploratory endpoint is to test the relative engraftment of CART-19 cells expressing TCR $\zeta$  or TCR $\zeta$ :4-1BB domains. It is recognized that there will be statistical power to detect only very large change in the ratio of CART-19 cells. The results of this study will provide information on the expected change in ratios of CART-19 cells from baseline to four weeks post dosing to provide guidance on which vector should be considered for a future larger study, as well as pilot data to allow determination of required samples sizes for that study.

With a total of 20 evaluable subjects in each cohort, there would be 80% power to detect a 0.76 standard deviation difference in the ratio between the two different CART-19 cell between just post dosing baseline values and values obtained from the week four apheresis, using a paired t-test at a 0.05 two-sided level of significance. With a total of seven evaluable subjects in each cohort, there would be 80% power to detect a 1.27 standard deviation difference in the CART-19 ratio under the same conditions.

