### **3 STUDY DESIGN**

#### **3.1 General Design**

We have designed a single-arm open-label phase I/IIa study to determine the safety, tolerability and engraftment potential of CART-19 T cells in patients with CD19+ hematologic malignancies. The general protocol schema is shown above in **figure 1** in section 1. All subjects will be dosed with CART-19 T cells. In all subjects treated to date, the CART-19 T cells contained only the TCR $\zeta$ :4-1BB transgene. A total of 72 subjects will be infused across “no allo”, “allo”, and CNS-3 cohorts. In order to infuse 72 patients, assuming a 20% drop out rate, we would enroll up to 86 patients.

A secondary objective is to determine if the 4-1BB transgene is superior to the TCR $\zeta$  only transgene. To test this, a cohort of 5 patients will be dosed with mixtures of TCR $\zeta$ :4-1BB and TCR $\zeta$  only cells, using a competitive repopulation strategy to determine the optimal signal transduction module in the chimeric receptor (**figure 13**). This cohort will proceed only after the 2 CARs to be compared are finalized. It is reasonable to assume that engineered T cells containing signaling domains that mimic physiologic signaling will function best in vivo, and therefore, we think that CART-19:TCR $\zeta$ :4-1BB will be superior to CART-19:TCR $\zeta$  only. **The null hypothesis is that they are equivalent.**

At entry, subjects will be staged and the suitability of their T cells for CART-19 manufacturing will be determined. Subjects in both the no allo and allo cohorts who have adequate T cells will be leukapheresed to obtain large numbers of peripheral blood mononuclear cells (PBMC) for CART-19 manufacturing. In each cohort, the subject is pheresed; however, in the allo cohort, T cells derived from donor engrafted cells may be collected from the subject. The T cells will be purified from the PBMC, transduced with CART-19 lentiviral vector, expanded in vitro and then frozen for future administration. Chemotherapy will then be given. Following tumor burden reassessment, CART-19 cells will be thawed and infused.

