### 5.3 Treatment Regimen

#### 5.3.1 Patients 1-72 (infused), including CNS3 cohort

CART-19 transduced T cells will be given, up to a total dose of  $1.5 \times 10^7$ - $5 \times 10^9$  ( $0.3 \times 10^6$ - $1.0 \times 10^8$ /kg)- total cells transduced with the 41BB-z vector. We will use the following schedule, starting with a 10x dose reduction but allowing for intra-patient dose escalation (see section 6.6):

- Day 0: 10% of total dose
- Day 1: 30% of total dose if patient is clinically stable from prior day's infusion

See section 6.6 for details on timing and doses of subsequent CART-19 infusions. The toxicities that would preclude the next dose of T cells are DLTs or GVHD attributable to the cell infusion, and not toxicities attributable to the prior chemotherapy, such as cytopenias. A DLT will prevent the infusion of the next dose, even if fully resolved by that time.

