Observation and monitoring of patients will continue on a monthly basis until 24 weeks after a cell infusion is given. In subjects given a mixture of CART-19 cells, the change in the ratio of the vector transduced cells to each other between baseline and week four will be evaluated. After two years, annual follow-up for lentiviral vector safety will be carried out under a separate destination protocol for 15 years post infusion in accordance with FDA guidelines for retroviral vectors.

72 subjects will be targeted for infusion in this study. We have observed a drop out rate of less than 20% or less due to disease progression or clinical deterioration between enrollment and initial infusion (this will take about 6-8 weeks for screening-apheresis to dosing). However, as we are eliminating the test expansion, we may increase this dropout rate by 5-15%. Thus, up to 86 subjects will be initially enrolled to allow our goal of 72 infusions.

All safety data after initial CART-19 infusion will be summarized regardless of whether patient receives subsequent CART-19 infusions or not (Section 6.6). Efficacy data will be summarized from initial CART-19 infusion to first documented relapse or end of follow-up, whichever occurs first. Additional analyses may be planned as needed.

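### Section 7.5's n=20 power figure should be 0.66 SD, not 0.76 SD, and no figure is given for the 5-patient mixture cohort that supplies the ratio

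*Combined protocol and SAP*

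**What the plan says.** Section 7.5 gives two power statements for the change in the ratio of the two CART-19 products between the post-dosing baseline and week four. The first is "With a total of 20 evaluable subjects in each cohort, there would be 80% power to detect a 0.76 standard deviation difference", with the test given as "using a paired t-test at a 0.05 two-sided level of significance". The second is "With a total of seven evaluable subjects in each cohort, there would be 80% power to detect a 1.27 standard deviation difference", under the same conditions. The section adds a caveat, "It is recognized that there will be statistical power to detect only very large change in the ratio of CART-19 cells", and says the results are meant "to provide guidance on which vector should be considered for a future larger study".

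Other sections fix who can supply the ratio:

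- Section 7.1 evaluates it only in recipients of both products: "In subjects given a mixture of CART-19 cells, the change in the ratio of the vector transduced cells to each other".
- Section 5.3.1 gives patients 1-72 "total cells transduced with the 41BB-z vector", so no ratio can be formed in them.
- Section 3.1 gives the only stated size of the mixture cohort: "a cohort of 5 patients will be dosed with mixtures of TCR" (the quote stops at the zeta symbol; the two products are the 4-1BB and the zeta-only constructs).
- Section 6.6 refers to the mixture recipients as subjects 15-20, which is six if counted inclusively.
- Section 5.3.2 puts this cohort on hold and requires a modified protocol and consent form, with IRB approval, before anyone in it is treated.

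Section 7.7 plans a Wilcoxon signed-rank test for the ratio. It does not say whether the test is exact and gives no significance level for it.

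**The concern.** The two statements in 7.5 claim the same test, alpha and power, so one calculation should reproduce both. It reproduces only the second.

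The sizes are also not those of the cohort concerned. The smallest size quoted is seven, so a reader would take 1.27 SD as the least favourable case, although the mixture cohort is smaller. The test used for power also differs from the test planned for analysis. The difference is small at n=20, but at n=5 it decides whether the 0.05 level can be reached at all.

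At stake is how the result would be read. Section 3.1 states a null hypothesis of equivalence for this comparison, and 7.5 wants the result to help choose a vector for a larger trial. A non-significant result from five patients could be taken as evidence of no difference when the analysis had little or no chance of showing one.

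**Working it through.** **Inputs.** From 7.5: paired t-test, two-sided alpha 0.05, power 80%, n = 20 and n = 7. From 3.1: n = 5. From 6.6, counted inclusively: n = 6. From 7.7: signed-rank test. Changes are taken as normal, with the effect d in units of the SD of the within-patient change.

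**Formula.** Power = P(|T| > t(0.975, n−1)), where T is noncentral t with n−1 degrees of freedom and noncentrality d√n. Solve for d at the required power.

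**The plan's own figures.**

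- n = 7: d = 1.273, and power at 1.27 SD is 79.8%. The stated 1.27 is reproduced, so this is the plan's method.
- n = 20: d = 0.660, not 0.76. Power at 0.76 SD is 89.7%, which is 9.7 points above the stated 80%.

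**Where 0.76 could come from.** At n = 20 it is close to the 90%-power value (0.764). As an 80%-power value it falls between n = 15 (0.778) and n = 16 (0.749). Other readings at n = 20 and 80% power do not give it:

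| Variant at n = 20 | Detectable d |
|---|---|
| One-sided 0.05 | 0.577 |
| Normal approximation | 0.626 |
| Two-sided 0.025 | 0.739 |
| Two-sided 0.01 | 0.838 |
| t-test value divided by √0.955 (signed-rank efficiency) | 0.676 |
| t-test value divided by √0.864 | 0.711 |
| Two-sample t, 20 per group | 0.909 |
| Two-sample t, 10 per group | 1.325 |

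Simulating the exact signed-rank test at n = 20 (4,000 data sets per effect) gave power of about 80% at 0.68 SD and 89% at 0.76 SD, so the change of test does not explain the figure either.

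**The mixture cohort, paired t-test, 80% power.**

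- n = 5: d = 1.68. Power is 57.5% at 1.27 SD and 25.9% at 0.76 SD.
- n = 6: d = 1.43.

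**The mixture cohort, exact signed-rank test.** The smallest two-sided p is 2/2^n.

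- n = 5: 2/32 = 0.0625. No outcome reaches 0.05, so power at that level is 0 for any effect.
- n = 6: 2/64 = 0.03125. The test rejects only if all six changes share a sign. For normal data the power is Φ(d)^6 + Φ(−d)^6. This equals 0.80 at d = 1.79, and at the t-test's 1.43 SD it is 62.3%.

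**Why exactness must be stated.** At n = 5 with all changes in one direction, W = 15. Its null mean is 5×6/4 = 7.5 and its null variance is 5×6×11/24 = 13.75. Then z = 7.5/√13.75 = 2.023, and the uncorrected normal approximation gives two-sided p = 0.043. The same data give 0.0625 exactly. Whether 0.05 can be reached therefore depends on a choice that 7.7 leaves open.

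**The case against.** The arithmetic at n = 20 is not in dispute, but it can fairly be said that little follows from it. No cohort of 20 able to supply a ratio is described, the sample size in 7.3 is not derived from 7.5, and the error understates power. The cohort is on hold while the choice of comparator is reconsidered, so a figure for five patients may describe a design that is never run. Section 7.5 already warns that only very large changes are detectable, 7.7 calls the analysis primarily descriptive, and an exploratory pilot need not give a power figure for every cohort. Section 7.7 also gives a reason for using the signed-rank test, its efficiency of more than 95% relative to the t-test for normal data. Finally, zero power at n = 5 holds only for an exact test judged at a 0.05 level carried over from 7.5.

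All of this bears on priority, and it is why the point ranks low. It does not make 0.76 correct, and it does not make sizes of 20 and seven describe a cohort of five. The efficiency argument does not help at n = 5, where the limit is the small number of possible sign patterns. The qualitative caveat does not tell a reader that the requirement is above 1.27 SD. The hold favours correcting the text during the redesign, before it is carried forward.

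**Conclusion.** The point holds, at low priority. The n = 20 statement in 7.5 is wrong as written: 80% power corresponds to 0.66 SD, and 0.76 SD is approximately the 90%-power value. The documents do not show which was intended. The n = 7 statement is right.

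Section 7.5 gives no detectable difference for the mixture cohort. At the stated size of 5, the paired t-test needs 1.68 SD. An exact two-sided signed-rank test cannot reach 0.05. If the size is 6, the requirements are 1.43 SD and 1.79 SD respectively.

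These values assume normally distributed changes, all patients evaluable and the 0.05 level of 7.5. The 0.0625 minimum does not need normality, only an exact test with five pairs. The ratio is a secondary or exploratory endpoint in a cohort that has not opened.

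**What to change.** In 7.5, replace 0.76 with 0.66, or keep 0.76 and change 80% to 90%.

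In the modification that 5.3.2 already requires:

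- State one mixture-cohort size, consistently in 3.1 and 6.6.
- Give in 7.5 the detectable difference for that size and for the test that will be used.
- State in 7.7 whether the signed-rank test is exact, and at what level it will be judged.
- If the size stays at 5 with an exact test, say that two-sided 0.05 cannot be reached and that the comparison is descriptive.

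As housekeeping, reconcile the week-four apheresis named in 7.5 with the Day 28 peripheral blood draw in 6.9 and with the schedule in 15.1, which marks leukapheresis only at about week −4.

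The cost is one number and some text in 3.1, 6.6, 7.5 and 7.7. Settling the cohort size is a design decision, but it belongs to the redesign already planned. This finding adds no patients or procedures.

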#### 7.6 Subject Population(s) for Analysis

The subject population to be analyzed for primary and secondary endpoints will include all patients infused with CART-19 cells.

A second population of patients will include all patients enrolled on study but who do not receive CART-19 cells. Reasons patients do not receive cell infusions are likely to include 1) ineffective

CONFIDENTIAL

transduction of autologous T cells; 2) rapid progression, clinical deterioration, and/or death between the time of enrollment and infusion; 3) subject withdrawal.

The number of patients enrolled versus the number of patients infused will be described and is a measure of the feasibility of this therapy for patients with various malignancies to be treated.

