    - Relapsed after prior autologous SCT.
  - e. B-cell prolymphocytic leukemia (PLL) with relapsed or residual disease after at least 1 prior therapy and not eligible for allogeneic SCT.
  - f. Diffuse large cell lymphoma or other high-grade NHL, previously identified as CD19+
    - Residual disease after primary therapy and not eligible for autologous SCT.
    - Relapsed after prior autologous SCT.
    - Beyond 1st CR with relapsed or persistent disease and not eligible or appropriate for conventional allogeneic or autologous SCT.
2. Age 1 to 24 years. Patients ages 22-24 will only be enrolled if they are currently being treated at CHOP or another pediatric facility/oncologist.

CONFIDENTIAL

3. Expected survival > 12 weeks
4. Creatinine < 2.5 mg/dl and less than 2.5x normal for age
5. ALT ≤ 5x normal
6. Bilirubin <2.0 mg/dl
7. Any relapse after prior SCT will make patient eligible regardless of other prior therapy.
8. Patients with relapsed disease after prior allogeneic SCT (myeloablative or non-myeloablative) will be eligible if they meet all other inclusion criteria and
  - a. Have no active GVHD and require no immunosuppression
  - b. Are more than 4 months from transplant (6 months at infusion; see Section 5.2)
9. For those patients who require leukapheresis for T cell collection (i.e. no previously collected product exists), adequate venous access for apheresis or eligible for appropriate catheter placement, and no other contraindications for leukapheresis.
10. Voluntary informed consent is given.
11. Patients with CNS3 disease will be eligible if CNS disease is responsive to therapy (at infusion, must meet criteria in Section 5.2) (see section 15.5 for definitions of CNS1, CNS2 and CNS3 disease)

NOTE on 1.a.vi – declines SCT: SCT is performed in patients with ALL in CR3, but the outcomes are problematic. Most data suggest about a 30% OS in the highly selected group of patients. A report which places this in context was published in JCO by Saarinen-Pihkala et al., looking at the overall (population-based) experience in CR3 ALL. Of 71 pts with ALL in CR3, OS after SCT was 30% and EFS 15%. Overall EFS of the 71 patients in CR3 was 7%. These numbers indicate that a decision to pursue a therapy other than SCT in CR3 ALL is rational, and that CART-19 therapy may offer a benefit to patients in this group.

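### Response and survival are planned only in infused patients, counted from infusion, with no companion analysis of everyone enrolled

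*Combined protocol and SAP*

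**What the plan says.** Section 7.6 defines two populations. The first carries the endpoints: "The subject population to be analyzed for primary and secondary endpoints will include all patients infused with CART-19 cells". The other is its complement: "A second population of patients will include all patients enrolled on study but who do not receive CART-19 cells". No endpoint is assigned to the second population, and the union of the two is not named as an analysis set.

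Section 3.3 makes Day 28 overall response the main efficacy endpoint. It sits among the secondary endpoints, as does overall survival (Sections 3.3 and 7.2.2), so both fall in the infused set. Section 7.1 gives the time frame: "Efficacy data will be summarized from initial CART-19 infusion to first documented relapse or end of follow-up, whichever occurs first".

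On losses before infusion, Section 7.1 reports dropout of 20% or less, "due to disease progression or clinical deterioration between enrollment and initial infusion (this will take about 6-8 weeks for screening-apheresis to dosing"). Section 7.6 lists "rapid progression, clinical deterioration, and/or death between the time of enrollment and infusion" alongside failed transduction and withdrawal. Section 3.1 sets the numbers: "In order to infuse 72 patients, assuming a 20% drop out rate, we would enroll up to 86 patients". Section 7.1 adds that, with the test expansion removed, "we may increase this dropout rate by 5-15" per cent.

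Two statements limit the issue. Section 7.6 promises to describe enrolled against infused numbers as a measure of feasibility. Sections 3.3, 7.5 and 7.7 treat efficacy as descriptive and leave its determination to a later study.

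**The concern.** A patient enters the trial at enrolment, but is counted for response and survival only if cells are manufactured, consent is not withdrawn, and disease or clinical state does not prevent infusion. Several of those conditions are related to prognosis. Patients who fail them would probably have done worse than average, and they leave the denominator before the clock starts.

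The results will then describe patients who were treated. Without a figure for all enrolled, readers may take them as the prospect facing a patient who is offered the trial, and that prospect is less favourable. The gap could also become permanent for survival. If vital status is not collected for non-infused patients during the trial, it may not be recoverable afterwards.

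**Working it through.** **1. Which set holds which patients.**

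| Population | Source | Endpoint analysis assigned |
|---|---|---|
| Infused | 7.6, first population | All primary and secondary endpoints |
| Enrolled, not infused | 7.6, second population | None |
| All enrolled | Not defined | Only the enrolled-versus-infused count |

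**2. The planned attrition.** The 86 in Section 3.1 reproduces as 72 × 1.20 = 86.4. At those numbers, 86 − 72 = 14 patients are not infused, a loss of 14/86 = 16.3%. A true 20% loss would need 72/(1 − 0.20) = 90 enrolled, or would leave 86 × 0.80 = 68.8 infused out of 86. Whether 86 is the right total is a separate matter. Here it only decides which infused fraction applies.

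**3. Effect on a response rate.** Let p be the rate among infused patients and f the fraction infused. Counting non-infused patients as non-responders, the all-enrolled rate is p × f. The documents state no expected p, so the values below are assumptions. The last two rows read the 5-15% in Section 7.1 as percentage points added to 20%, which is also an assumption.

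| Loss before infusion | f | p = 60% | p = 80% | p = 90% |
|---|---|---|---|---|
| 16.3% (72/86) | 0.837 | 50% | 67% | 75% |
| 20% | 0.80 | 48% | 64% | 72% |
| 25% | 0.75 | 45% | 60% | 67.5% |
| 35% | 0.65 | 39% | 52% | 58.5% |

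For scale against sampling error, take 58 responders. 58/72 = 81% (exact 95% CI 70-89%) becomes 58/86 = 67% (57-77%). The shift of about 13 points exceeds the half-width of either interval, which is about 10.

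**4. Which patients f applies to.** Section 3.3 scores partial and complete response in subjects with active disease. Subjects with minimal residual disease or in remission have other endpoints. The documents do not give this split, and the promised counts are not broken down by it. Using 72/86 for the response endpoint therefore assumes the same attrition in active disease as in the whole trial.

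**5. Survival.** The count of enrolled and infused patients cannot rebuild a survival curve from enrolment, because that needs death dates for patients who were not infused. Three sections bear on whether these will exist:

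- Section 4.4.2 follows subjects for survival in general terms.
- Section 8.4.5 discontinues subjects who become unable to receive cells.
- Section 6.12 covers subjects leaving primary follow-up in remission, with contacts timed from infusion.

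Read together, they do not clearly assure vital status for the non-infused.

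For order of magnitude only, suppose exponential survival from enrolment with median m, and a gap t of 6 to 8 weeks (1.38 to 1.84 months). The share dying in the gap is 1 − exp(−ln 2 × t/m):

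- m = 6 months: 15-19%
- m = 12 months: 8-10%
- m = 24 months: 4-5%

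These medians are assumptions. The requirement for expected survival beyond 12 weeks (Section 4.1) should push the true early losses lower.

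**The case against.** The strongest reply is that this is a phase I/IIa study of safety, feasibility and engraftment. Efficacy has no hypothesis, power or comparator, and Section 7.5 leaves it to another trial. An estimate in treated patients from the day of treatment is a legitimate target, and starting the clock there is not in itself an immortal-time error. Attrition is disclosed in Section 7.6, and Section 7.1 leaves room for further analyses. All of this stands. It lowers the severity and is the reason to keep the infused-set analysis. It does not supply the missing denominator: the count allows only a crude rescaling of response and none of survival, and an option to do more commits no one to doing it.

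Three stronger readings are tempting, and the documents do not support them.

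- A reader might infer that patients must survive 6-8 weeks without progression to be counted. The condition is reaching infusion. Active disease that is stable or responding is allowed at entry (Section 4.1). The disease-response criterion for infusion in Section 5.2 is not visible in the public copy. Cells collected before enrolment (Section 6.4) can shorten the wait.
- A reader might set the planned results against the transplant figures in the Section 4.1 note, which says "Most data suggest about a 30% OS in the highly selected group of patients" and gives 7% event-free survival for all 71 patients in third remission. That note is a rationale for eligibility, and no section plans a comparison with it. The 30% and the 7% are different endpoints; the like-for-like pair is 15% against 7% event-free survival. The note also covers only ALL in third remission, a narrower group than this trial enrols.
- A reader might infer that overall survival is explicitly timed from infusion. Section 7.1 says so for efficacy data in general. Taken literally, that sentence also ends follow-up at relapse, which cannot be meant for overall survival. No section states a separate start date for it.

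**Conclusion.** The point holds as a gap in the plan: an all-enrolled companion analysis is missing. As written, Day 28 response and, on the natural reading of Section 7.1, overall survival will be reported only for patients who reached infusion, typically about 6-8 weeks after screening and apheresis. Those results are valid for treated patients but do not describe what a patient entering the trial can expect.

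For response, the size is a multiplier of 0.84 at the planned numbers, 0.80 at 20% loss, and 0.75 to 0.65 if dropout rises to 25-35%. This rests on equal attrition in active disease, on non-infused patients counting as non-responders, and on reading the added dropout as percentage points. The upper end is a possibility that the plan raises, since observed dropout was 20% or less. For survival, the documents do not support a firm figure.

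Severity is moderate to low, because efficacy here is secondary and descriptive.

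**What to change.** Keep the infused-set analyses and make three additions.

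1. In Section 7.6, define an all-enrolled set.
2. Beside the infused-set results, report Day 28 response among enrolled subjects with active disease at enrolment, counting non-infused subjects as non-responders, and report overall survival from the date of enrolment. Say how subjects who enter remission on chemotherapy before infusion are counted, since Section 3.3 classifies subjects by disease status at treatment.
3. Add one sentence to Sections 4.4.2 and 6.12 extending the survival contacts to subjects who are enrolled but not infused.

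The third item is a change to protocol procedures as well as to the analysis text. It concerns about 14 subjects at the planned numbers, or 17 to 30 of 86 at 20-35% loss (86 × 0.20 = 17.2; 86 × 0.35 = 30.1). The cost is a modest number of vital-status contacts, a little analysis work, and companion figures that will look less favourable than the infused-set ones.
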